BNL	xx (xx.x%)	xx (xx.x%)	xx (xx.x%)	xx (xx.x%)	xx (xx.x%)	xx (xx.x%)
WNL	xx (xx.x%)	xx (xx.x%)	xx (xx.x%)	xx (xx.x%)	xx (xx.x%)	xx (xx.x%)
ANL	xx (xx.x%)	xx (xx.x%)	xx (xx.x%)	xx (xx.x%)	xx (xx.x%)	xx (xx.x%)

Note: BNL=Below Normal Limit, WNL=Within Normal Limits, ANL=Above Normal Limit.

No imputation of missing values. Baseline is the latest recorded value prior to first dose of study drug. "Latest Follow-up" visit includes the latest available follow-up information for each subject from the 3-Week or 5-Week Follow-up visits.

SOURCE: USERNAME\SPONSOR\PROJECT\JOBNAME (DATE,TIME)

Table to include the same lab tests used in Table 14.3.1.4.1.1.

Table 14.3.1.4.2.1: Summary of Chemistry Laboratory Results
(Safety Population)
(Page 1 of xx)

<Test Name> (<units>)	Placebo (N=xxx)	Serlopitant 5 mg (N=xxx)
Baseline		
n	xx	xx
Mean	xx.x	xx.x
SD	xx.xx	xx.xx
Median	xx.x	xx.x
Min. to Max.	xx to xx	xx to xx
Week 2		
n	xx	xx
Mean	xx.x	xx.x
SD	xx.xx	xx.xx
Median	xx.x	xx.x
Min. to Max.	xx to xx	xx to xx
Absolute Change from Baseline		
n	xx	xx
Mean	xx.x	xx.x
SD	xx.xx	xx.xx
Median	xx.x	xx.x
Min. to Max.	xx to xx	xx to xx

Note: No imputation of missing values. Baseline is the latest recorded value prior to first dose of study drug. Change calculated as post-baseline – baseline.

“Latest Follow-up” visit includes the latest available follow-up information for each subject from the 3-Week or 5-Week Follow-up visits.

SOURCE: USERNAME\SPONSOR\PROJECT\JOBNAME (DATE,TIME)

Table to include post-baseline visits of “Week 2”, “Week 10”, “3-Week Follow-up”, “5-Week Follow-up”, “Latest Follow-up”.

Table to include following lab tests: “ALBUMIN”, “ALKALINE PHOSPHATASE”, “ALT”, “AST”, “BICARBONATE”, “BILIRUBIN, TOTAL”, “BUN”, “CALCIUM”, “CHLORIDE”, “CHOLESTEROL, TOTAL”, “CREATININE”, “GLUCOSE, RANDOM”, “HDL-CHOLESTEROL”, “LDH”, “LDL-CHOLESTEROL”, “MAGNESIUM”, “PHOSPHORUS”, “POTASSIUM”, “PROTEIN, TOTAL”, “SODIUM”, “TRIGLYCERIDES”, “URIC ACID”.

CONFIDENTIAL

Table 14.3.1.4.2.2: Shift Summary of Chemistry Laboratory Results
(Safety Population)
(Page 1 of xx)

<Test Name> (<units>)	Placebo (N=xxx)			Serlopitant 5 mg (N=xxx)		
		Week 2			Week 2	
Baseline	BNL	WNL	ANL	BNL	WNL	ANL
BNL	xx (xx.x%)	xx (xx.x%)	xx (xx.x%)	xx (xx.x%)	xx (xx.x%)	xx (xx.x%)
WNL	xx (xx.x%)	xx (xx.x%)	xx (xx.x%)	xx (xx.x%)	xx (xx.x%)	xx (xx.x%)
ANL	xx (xx.x%)	xx (xx.x%)	xx (xx.x%)	xx (xx.x%)	xx (xx.x%)	xx (xx.x%)
	Week 10			Week 10		
Baseline	BNL	WNL	ANL	BNL	WNL	ANL
BNL	xx (xx.x%)	xx (xx.x%)	xx (xx.x%)	xx (xx.x%)	xx (xx.x%)	xx (xx.x%)
WNL	xx (xx.x%)	xx (xx.x%)	xx (xx.x%)	xx (xx.x%)	xx (xx.x%)	xx (xx.x%)
ANL	xx (xx.x%)	xx (xx.x%)	xx (xx.x%)	xx (xx.x%)	xx (xx.x%)	xx (xx.x%)
	3-Week Follow-up			3-Week Follow-up		
Baseline	BNL	WNL	ANL	BNL	WNL	ANL
BNL	xx (xx.x%)	xx (xx.x%)	xx (xx.x%)	xx (xx.x%)	xx (xx.x%)	xx (xx.x%)
WNL	xx (xx.x%)	xx (xx.x%)	xx (xx.x%)	xx (xx.x%)	xx (xx.x%)	xx (xx.x%)
ANL	xx (xx.x%)	xx (xx.x%)	xx (xx.x%)	xx (xx.x%)	xx (xx.x%)	xx (xx.x%)
	5-Week Follow-up			5-Week Follow-up		
Baseline	BNL	WNL	ANL	BNL	WNL	ANL
BNL	xx (xx.x%)	xx (xx.x%)	xx (xx.x%)	xx (xx.x%)	xx (xx.x%)	xx (xx.x%)
WNL	xx (xx.x%)	xx (xx.x%)	xx (xx.x%)	xx (xx.x%)	xx (xx.x%)	xx (xx.x%)
ANL	xx (xx.x%)	xx (xx.x%)	xx (xx.x%)	xx (xx.x%)	xx (xx.x%)	xx (xx.x%)
	Latest Follow-up			Latest Follow-up		
Baseline	BNL	WNL	ANL	BNL	WNL	ANL
BNL	xx (xx.x%)	xx (xx.x%)	xx (xx.x%)	xx (xx.x%)	xx (xx.x%)	xx (xx.x%)
WNL	xx (xx.x%)	xx (xx.x%)	xx (xx.x%)	xx (xx.x%)	xx (xx.x%)	xx (xx.x%)
ANL	xx (xx.x%)	xx (xx.x%)	xx (xx.x%)	xx (xx.x%)	xx (xx.x%)	xx (xx.x%)

Note: BNL=Below Normal Limit, WNL=Within Normal Limits, ANL=Above Normal Limit.

No imputation of missing values. Baseline is the latest recorded value prior to first dose of study drug. "Latest Follow-up" visit includes the latest available follow-up information for each subject from the 3-Week or 5-Week Follow-up visits.

SOURCE: USERNAME\SPONSOR\PROJECT\JOBNAME (DATE,TIME)

Table to include the same lab tests used in Table 14.3.1.4.2.1.

Table 14.3.1.4.3.1.1: Summary of Endocrine/Reproductive Endocrine Laboratory Results
(Safety Population)
(Page 1 of xx)

<Test Name> (<units>)	Placebo (N=xxx)	Serlopitant 5 mg (N=xxx)
Baseline		
n	xx	xx
Mean	xx.x	xx.x
SD	xx.xx	xx.xx
Median	xx.x	xx.x
Min. to Max.	xx to xx	xx to xx
Week 10		
n	xx	xx
Mean	xx.x	xx.x
SD	xx.xx	xx.xx
Median	xx.x	xx.x
Min. to Max.	xx to xx	xx to xx
Absolute Change from Baseline		
n	xx	xx
Mean	xx.x	xx.x
SD	xx.xx	xx.xx
Median	xx.x	xx.x
Min. to Max.	xx to xx	xx to xx

Note: No imputation of missing values. Baseline is the latest recorded value prior to first dose of study drug. Change calculated as post-baseline – baseline.
 “Latest Follow-up” visit includes the latest available follow-up information for each subject from the 3-Week or 5-Week Follow-up visits.
 SOURCE: USERNAME\SPONSOR\PROJECT\JOBNAME (DATE,TIME)

Table to include post-baseline visits of “Week 10”, “3-Week Follow-up”, “5-Week Follow-up”, “Latest Follow-up”.

Table to include following lab tests: “TSH ULTRASENSITIVE”, “THYROXINE, FREE”, “CORTISOL, SERUM RANDOM”, “ACTH, PLASMA”, “ANTI-MULLERIAN HORMONE”, “FSH”, “ESTRADIOL”, “LUTEINIZING HORMONE”, “PROGESTERONE”.

CONFIDENTIAL

Table 14.3.1.4.3.1.2: Summary of Reproductive Endocrine Laboratory Results
 (Safety Population – Females Using Hormonal Contraception/Therapy)
 (Page 1 of xx)

<Test Name> (<units>)	Placebo (N=xxx)	Serlopitant 5 mg (N=xxx)
Baseline		
n	xx	xx
Mean	xx.x	xx.x
SD	xx.xx	xx.xx
Median	xx.x	xx.x
Min. to Max.	xx to xx	xx to xx
Week 10		
n	xx	xx
Mean	xx.x	xx.x
SD	xx.xx	xx.xx
Median	xx.x	xx.x
Min. to Max.	xx to xx	xx to xx
Absolute Change from Baseline		
n	xx	xx
Mean	xx.x	xx.x
SD	xx.xx	xx.xx
Median	xx.x	xx.x
Min. to Max.	xx to xx	xx to xx

Note: No imputation of missing values. Baseline is the latest recorded value prior to first dose of study drug. Change calculated as post-baseline – baseline.
 “Latest Follow-up” visit includes the latest available follow-up information for each subject from the 3-Week or 5-Week Follow-up visits.
 SOURCE: USERNAME\SPONSOR\PROJECT\JOBNAME (DATE,TIME)

Table to include post-baseline visits of “Week 10”, “3-Week Follow-up”, “5-Week Follow-up”, “Latest Follow-up”.

Table to include following lab tests: “ANTI-MULLERIAN HORMONE”, “FSH”, “ESTRADIOL”, “LUTEINIZING HORMONE”, “PROGESTERONE”.

CONFIDENTIAL

Table 14.3.1.4.3.1.3: Summary of Reproductive Endocrine Laboratory Results
(Safety Population – Females Not Using Hormonal Contraception/Therapy)
(Page 1 of xx)

<Test Name> (<units>)	Placebo (N=xxx)	Serlopitant 5 mg (N=xxx)
Baseline		
n	xx	xx
Mean	xx.x	xx.x
SD	xx.xx	xx.xx
Median	xx.x	xx.x
Min. to Max.	xx to xx	xx to xx
Week 10		
n	xx	xx
Mean	xx.x	xx.x
SD	xx.xx	xx.xx
Median	xx.x	xx.x
Min. to Max.	xx to xx	xx to xx
Absolute Change from Baseline		
n	xx	xx
Mean	xx.x	xx.x
SD	xx.xx	xx.xx
Median	xx.x	xx.x
Min. to Max.	xx to xx	xx to xx

Note: No imputation of missing values. Baseline is the latest recorded value prior to first dose of study drug. Change calculated as post-baseline – baseline.
 “Latest Follow-up” visit includes the latest available follow-up information for each subject from the 3-Week or 5-Week Follow-up visits.
 SOURCE: USERNAME\SPONSOR\PROJECT\JOBNAME (DATE,TIME)

Table to include post-baseline visits of “Week 10”, “3-Week Follow-up”, “5-Week Follow-up”, “Latest Follow-up”.

Table to include following lab tests: “ANTI-MULLERIAN HORMONE”, “FSH”, “ESTRADIOL”, “LUTEINIZING HORMONE”, “PROGESTERONE”.

CONFIDENTIAL

Table 14.3.1.4.3.2: Shift Summary of Endocrine/Reproductive Endocrine Laboratory Results
(Safety Population)
(Page 1 of xx)

<Test Name> (<units>)	Placebo (N=xxx)			Serlopitant 5 mg (N=xxx)		
	Week 10			Week 10		
Baseline	BNL	WNL	ANL	BNL	WNL	ANL
BNL	xx (xx.x%)	xx (xx.x%)	xx (xx.x%)	xx (xx.x%)	xx (xx.x%)	xx (xx.x%)
WNL	xx (xx.x%)	xx (xx.x%)	xx (xx.x%)	xx (xx.x%)	xx (xx.x%)	xx (xx.x%)
ANL	xx (xx.x%)	xx (xx.x%)	xx (xx.x%)	xx (xx.x%)	xx (xx.x%)	xx (xx.x%)
3-Week Follow-up			3-Week Follow-up			
Baseline	BNL	WNL	ANL	BNL	WNL	ANL
BNL	xx (xx.x%)	xx (xx.x%)	xx (xx.x%)	xx (xx.x%)	xx (xx.x%)	xx (xx.x%)
WNL	xx (xx.x%)	xx (xx.x%)	xx (xx.x%)	xx (xx.x%)	xx (xx.x%)	xx (xx.x%)
ANL	xx (xx.x%)	xx (xx.x%)	xx (xx.x%)	xx (xx.x%)	xx (xx.x%)	xx (xx.x%)
5-Week Follow-up			5-Week Follow-up			
Baseline	BNL	WNL	ANL	BNL	WNL	ANL
BNL	xx (xx.x%)	xx (xx.x%)	xx (xx.x%)	xx (xx.x%)	xx (xx.x%)	xx (xx.x%)
WNL	xx (xx.x%)	xx (xx.x%)	xx (xx.x%)	xx (xx.x%)	xx (xx.x%)	xx (xx.x%)
ANL	xx (xx.x%)	xx (xx.x%)	xx (xx.x%)	xx (xx.x%)	xx (xx.x%)	xx (xx.x%)
Latest Follow-up			Latest Follow-up			
Baseline	BNL	WNL	ANL	BNL	WNL	ANL
BNL	xx (xx.x%)	xx (xx.x%)	xx (xx.x%)	xx (xx.x%)	xx (xx.x%)	xx (xx.x%)
WNL	xx (xx.x%)	xx (xx.x%)	xx (xx.x%)	xx (xx.x%)	xx (xx.x%)	xx (xx.x%)
ANL	xx (xx.x%)	xx (xx.x%)	xx (xx.x%)	xx (xx.x%)	xx (xx.x%)	xx (xx.x%)

Note: BNL=Below Normal Limit, WNL=Within Normal Limits, ANL=Above Normal Limit.

No imputation of missing values. Baseline is the latest recorded value prior to first dose of study drug. "Latest Follow-up" visit includes the latest available follow-up information for each subject from the 3-Week or 5-Week Follow-up visits.

SOURCE: USERNAME\SPONSOR\PROJECT\JOBNAME (DATE,TIME)

Table to include following lab tests: "TSH ULTRASENSITIVE", "THYROXINE, FREE", "CORTISOL, SERUM RANDOM", "ACTH, PLASMA", "ANTI-MULLERIAN HORMONE".

CONFIDENTIAL

Table 14.3.1.5.1.1: Summary of Treatment-Emergent Electrocardiogram (ECG) Parameter Abnormalities
(Safety Population)
(Page 1 of 2)

	Placebo (N=xxx)	Serlopitant 5 mg (N=xxx)
Number of Subjects with Treatment-Emergent ECG Results	xxx	xxx
PR Interval		
> 200 msec	xx (xx.x%)	xx (xx.x%)
> 220 msec	xx (xx.x%)	xx (xx.x%)
Change from Baseline in PR Interval		
>= 25% and > 200 msec	xx (xx.x%)	xx (xx.x%)
QRS Interval		
> 110 msec	xx (xx.x%)	xx (xx.x%)
> 120 msec	xx (xx.x%)	xx (xx.x%)
Change from Baseline in QRS Interval		
>= 25% and > 110 msec	xx (xx.x%)	xx (xx.x%)
>= 25% and > 120 msec	xx (xx.x%)	xx (xx.x%)
QTcF Interval		
> 450 - 470 msec	xx (xx.x%)	xx (xx.x%)
> 470 - 500 msec	xx (xx.x%)	xx (xx.x%)
> 500 msec	xx (xx.x%)	xx (xx.x%)
Change from Baseline in QTcF Interval		
> 30 - 60 msec	xx (xx.x%)	xx (xx.x%)
> 60 msec	xx (xx.x%)	xx (xx.x%)
QTcF Interval > 500 msec and Change from Baseline > 60 msec	xx (xx.x%)	xx (xx.x%)

Note: No imputation of missing values. Baseline is the latest recorded value prior to first dose of study drug. Change calculated as post-baseline – baseline.
SOURCE: USERNAME\SPONSOR\PROJECT\JOBNAME (DATE,TIME)

CONFIDENTIAL

Table 14.3.1.5.1.1: Summary of Treatment-Emergent Electrocardiogram (ECG) Abnormalities
(Safety Population)
(Page 2 of 2)

	Placebo (N=xxx)	Serlopitant 5 mg (N=xxx)
Number of Subjects with Treatment-Emergent ECG Results	xxx	xxx
QTcB Interval		
> 450 - 470 msec	xx (xx.x%)	xx (xx.x%)
> 470 - 500 msec	xx (xx.x%)	xx (xx.x%)
> 500 msec	xx (xx.x%)	xx (xx.x%)
Change from Baseline in QTcB Interval		
> 30 - 60 msec	xx (xx.x%)	xx (xx.x%)
> 60 msec	xx (xx.x%)	xx (xx.x%)
QTcB Interval > 500 msec and Change from Baseline > 60 msec	xx (xx.x%)	xx (xx.x%)

Note: No imputation of missing values. Baseline is the latest recorded value prior to first dose of study drug. Change calculated as post-baseline – baseline.
SOURCE: USERNAME\SPONSOR\PROJECT\JOBNAME (DATE,TIME)

Table 14.3.1.5.1.2: Summary of Electrocardiogram Parameters
(Safety Population)
(Page 1 of xx)

<Parameter> (<units>)	Placebo (N=xxx)	Serlopitant 5 mg (N=xxx)
Baseline		
n	xx	xx
Mean	xx.x	xx.x
SD	xx.xx	xx.xx
Median	xx.x	xx.x
Min. to Max.	xx to xx	xx to xx
Week 2		
n	xx	xx
Mean	xx.x	xx.x
SD	xx.xx	xx.xx
Median	xx.x	xx.x
Min. to Max.	xx to xx	xx to xx
Absolute Change from Baseline		
n	xx	xx
Mean	xx.x	xx.x
SD	xx.xx	xx.xx
Median	xx.x	xx.x
Min. to Max.	xx to xx	xx to xx

Note: No imputation of missing values. Baseline is the latest recorded value prior to first dose of study drug. Change calculated as post-baseline – baseline.

“Latest Follow-up” visit includes the latest available follow-up information for each subject from the 3-Week or 5-Week Follow-up visits.

SOURCE: USERNAME/SPONSOR/PROJECT/JOBNAME (DATE,TIME)

Table to include parameters “ECG Mean Heart Rate (beats/min)”, “PR Interval, Aggregate (msec)”, “QRS Duration, Aggregate (msec)”, “QT Interval, Aggregate (msec)”, “QTcB Interval, Aggregate (msec)”, “QTcF Interval, Aggregate (msec)”, “RR Interval, Aggregate (msec)”.

Table to include post-baseline visits of “Week 2”, “Week 4”, “Week 10”, “3-Week Follow-up”, “5-Week Follow-up”, “Latest Follow-up”.

CONFIDENTIAL

Table 14.3.1.5.1.3: Shift Summary of Overall Electrocardiogram (ECG) Assessments
(Safety Population)
(Page 1 of 2)

Overall ECG Assessment (per Investigator)	Placebo (N=xxx)			Serlopitant 5 mg (N=xxx)		
	Week 2			Week 2		
Baseline	Normal	Abnormal, NCS	Abnormal, CS	Normal	Abnormal, NCS	Abnormal, CS
Normal	xx (xx.x%)	xx (xx.x%)	xx (xx.x%)	xx (xx.x%)	xx (xx.x%)	xx (xx.x%)
Abnormal, NCS	xx (xx.x%)	xx (xx.x%)	xx (xx.x%)	xx (xx.x%)	xx (xx.x%)	xx (xx.x%)
Abnormal, CS	xx (xx.x%)	xx (xx.x%)	xx (xx.x%)	xx (xx.x%)	xx (xx.x%)	xx (xx.x%)
	Week 4			Week 4		
Baseline	Normal	Abnormal, NCS	Abnormal, CS	Normal	Abnormal, NCS	Abnormal, CS
Normal	xx (xx.x%)	xx (xx.x%)	xx (xx.x%)	xx (xx.x%)	xx (xx.x%)	xx (xx.x%)
Abnormal, NCS	xx (xx.x%)	xx (xx.x%)	xx (xx.x%)	xx (xx.x%)	xx (xx.x%)	xx (xx.x%)
Abnormal, CS	xx (xx.x%)	xx (xx.x%)	xx (xx.x%)	xx (xx.x%)	xx (xx.x%)	xx (xx.x%)
	Week 10			Week 10		
Baseline	Normal	Abnormal, NCS	Abnormal, CS	Normal	Abnormal, NCS	Abnormal, CS
Normal	xx (xx.x%)	xx (xx.x%)	xx (xx.x%)	xx (xx.x%)	xx (xx.x%)	xx (xx.x%)
Abnormal, NCS	xx (xx.x%)	xx (xx.x%)	xx (xx.x%)	xx (xx.x%)	xx (xx.x%)	xx (xx.x%)
Abnormal, CS	xx (xx.x%)	xx (xx.x%)	xx (xx.x%)	xx (xx.x%)	xx (xx.x%)	xx (xx.x%)
	3-Week Follow-up			3-Week Follow-up		
Baseline	Normal	Abnormal, NCS	Abnormal, CS	Normal	Abnormal, NCS	Abnormal, CS
Normal	xx (xx.x%)	xx (xx.x%)	xx (xx.x%)	xx (xx.x%)	xx (xx.x%)	xx (xx.x%)
Abnormal, NCS	xx (xx.x%)	xx (xx.x%)	xx (xx.x%)	xx (xx.x%)	xx (xx.x%)	xx (xx.x%)
Abnormal, CS	xx (xx.x%)	xx (xx.x%)	xx (xx.x%)	xx (xx.x%)	xx (xx.x%)	xx (xx.x%)
	5-Week Follow-up			5-Week Follow-up		
Baseline	Normal	Abnormal, NCS	Abnormal, CS	Normal	Abnormal, NCS	Abnormal, CS
Normal	xx (xx.x%)	xx (xx.x%)	xx (xx.x%)	xx (xx.x%)	xx (xx.x%)	xx (xx.x%)
Abnormal, NCS	xx (xx.x%)	xx (xx.x%)	xx (xx.x%)	xx (xx.x%)	xx (xx.x%)	xx (xx.x%)
Abnormal, CS	xx (xx.x%)	xx (xx.x%)	xx (xx.x%)	xx (xx.x%)	xx (xx.x%)	xx (xx.x%)

Note: No imputation of missing values. Baseline is the latest recorded value prior to first dose of study drug. "Latest Follow-up" visit includes the latest available follow-up information for each subject from the 3-Week or 5-Week Follow-up visits.

NCS=Not Clinically Significant; CS=Clinically Significant.

SOURCE: USERNAME\SPONSOR\PROJECT\JOBNAME (DATE,TIME)

CONFIDENTIAL

Table 14.3.1.5.1.3: Shift Summary of Overall Electrocardiogram (ECG) Assessments
(Safety Population)
(Page 2 of 2)

Overall ECG Assessment (per Investigator)	Placebo (N=xxx)			Serlopitant 5 mg (N=xxx)			
	Baseline	Latest Follow-up			Latest Follow-up		
		Normal	Abnormal, NCS	Abnormal, CS	Normal	Abnormal, NCS	Abnormal, CS
Normal	xx (xx.x%)	xx (xx.x%)	xx (xx.x%)	xx (xx.x%)	xx (xx.x%)	xx (xx.x%)	
Abnormal, NCS	xx (xx.x%)	xx (xx.x%)	xx (xx.x%)	xx (xx.x%)	xx (xx.x%)	xx (xx.x%)	
Abnormal, CS	xx (xx.x%)	xx (xx.x%)	xx (xx.x%)	xx (xx.x%)	xx (xx.x%)	xx (xx.x%)	

Note: No imputation of missing values. Baseline is the latest recorded value prior to first dose of study drug. "Latest Follow-up" visit includes the latest available follow-up information for each subject from the 3-Week or 5-Week Follow-up visits.

NCS=Not Clinically Significant; CS=Clinically Significant.

SOURCE: USERNAME/SPONSOR/PROJECT/JOBNAME (DATE,TIME)

Table 14.3.1.6.1: Summary of Vital Signs
(Safety Population)
(Page 1 of xx)

<Parameter> (<units>)	Placebo (N=xxx)	Serlopitant 5 mg (N=xxx)
Baseline		
n	xx	xx
Mean	xx.x	xx.x
SD	xx.xx	xx.xx
Median	xx.x	xx.x
Min. to Max.	xx to xx	xx to xx
Week 2		
n	xx	xx
Mean	xx.x	xx.x
SD	xx.xx	xx.xx
Median	xx.x	xx.x
Min. to Max.	xx to xx	xx to xx
Absolute Change from Baseline		
n	xx	xx
Mean	xx.x	xx.x
SD	xx.xx	xx.xx
Median	xx.x	xx.x
Min. to Max.	xx to xx	xx to xx

Note: Baseline is the latest recorded value prior to first dose of study drug. Change calculated as post-baseline – baseline. “Latest Follow-up” visit includes the latest available follow-up information for each subject from the 3-Week or 5-Week Follow-up visits.

SOURCE: USERNAME\SPONSOR\PROJECT\JOBNAME (DATE,TIME)

Table to include parameters in following order: “Temperature (degrees Celsius)”, “Respiration Rate (breaths/min)”, “Heart Rate (beats/min)”, “Systolic Blood Pressure (mmHg)”, “Diastolic Blood Pressure (mmHg)”.

Table to include post-baseline visits of “Week 2”, “Week 4”, “Week 6”, “Week 10”, “3-Week Follow-up”, “5-Week Follow-up”, “Latest Follow-up”.

Table 14.3.1.7.1: Summary of Hospital Anxiety and Depression Scale (HADS)
(Safety Population)
(Page 1 of xx)

<Subscale>	Placebo (N=xxx)	Serlopitant 5 mg (N=xxx)
Baseline		
n	xx	xx
Mean	xx.x	xx.x
SD	xx.xx	xx.xx
Median	xx.x	xx.x
Min. to Max.	xx to xx	xx to xx
Week 4		
n	xx	xx
Mean	xx.x	xx.x
SD	xx.xx	xx.xx
Median	xx.x	xx.x
Min. to Max.	xx to xx	xx to xx
Absolute Change from Baseline		
n	xx	xx
Mean	xx.x	xx.x
SD	xx.xx	xx.xx
Median	xx.x	xx.x
Min. to Max.	xx to xx	xx to xx

Note: Baseline is the latest recorded value prior to first dose of study drug. Change calculated as post-baseline – baseline. “Latest Follow-up” visit includes the latest available follow-up information for each subject from the 3-Week or 5-Week Follow-up visits.

SOURCE: USERNAME\SPONSOR\PROJECT\JOBNAME (DATE,TIME)

Table to include subscales in following order: “Anxiety Subscale”, “Depression Subscale”.

Table to include post-baseline visits of “Week 4”, “Week 10”, “3-Week Follow-up”, “5-Week Follow-up”, “Latest Follow-up”.

Table 14.3.1.8.1: Summary of Epworth Sleepiness Scale (ESS)
(Safety Population)
(Page 1 of xx)

	Placebo (N=xxx)	Serlopitant 5 mg (N=xxx)
ESS		
Baseline		
n	xx	xx
Mean	xx.x	xx.x
SD	xx.xx	xx.xx
Median	xx.x	xx.x
Min. to Max.	xx to xx	xx to xx
Week 4		
n	xx	xx
Mean	xx.x	xx.x
SD	xx.xx	xx.xx
Median	xx.x	xx.x
Min. to Max.	xx to xx	xx to xx
Absolute Change from Baseline		
n	xx	xx
Mean	xx.x	xx.x
SD	xx.xx	xx.xx
Median	xx.x	xx.x
Min. to Max.	xx to xx	xx to xx

Note: Baseline is the latest recorded value prior to first dose of study drug. Change calculated as post-baseline – baseline. “Latest Follow-up” visit includes the latest available follow-up information for each subject from the 3-Week or 5-Week Follow-up visits.

SOURCE: USERNAME\SPONSOR\PROJECT\JOBNAME (DATE,TIME)

Table to include post-baseline visits of “Week 4”, “Week 10”, “3-Week Follow-up”, “5-Week Follow-up”, “Latest Follow-up”.

CONFIDENTIAL

Table 14.3.1.9: Summary of Pharmacokinetic Concentrations
(Safety Population)

<Analyte> (<units>)	Placebo (N=xxx)	Serlopitant 5 mg (N=xxx)
Week 2		
n	xx	xx
Mean	xx.x	xx.x
SD	xx.xx	xx.xx
Median	xx.x	xx.x
Min. to Max.	xx to xx	xx to xx
Week 4		
n	xx	xx
Mean	xx.x	xx.x
SD	xx.xx	xx.xx
Median	xx.x	xx.x
Min. to Max.	xx to xx	xx to xx
Week 10		
n	xx	xx
Mean	xx.x	xx.x
SD	xx.xx	xx.xx
Median	xx.x	xx.x
Min. to Max.	xx to xx	xx to xx

Note: No imputation of missing values.

SOURCE: USERNAME/SPONSOR/PROJECT/JOBNAME (DATE,TIME)

Table to include analytes in following order: “M1/M1a”, “M2/M2a”, “M3”, “Serlopitant”.

CONFIDENTIAL

Table 14.3.1.10: Summary of Menstrual Cycles
(Safety Population)

	Placebo (N=xxx)	Serlopitant 5 mg (N=xxx)
Number of Menstrual Cycles		
n	xx	xx
Mean	xx.x	xx.x
SD	xx.xx	xx.xx
Median	xx.x	xx.x
Min. to Max.	xx to xx	xx to xx
Duration of Menstrual Cycles		
n	xx	xx
Mean	xx.x	xx.x
SD	xx.xx	xx.xx
Median	xx.x	xx.x
Min. to Max.	xx to xx	xx to xx

Note: No imputation of missing values.

SOURCE: USERNAME\SPONSOR\PROJECT\JOBNAME (DATE,TIME)

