5.6 Study Drug Discontinuation

Subjects should be discontinued from study drug treatment in the following situations:

- A female subject desires to become pregnant at the current time, stops contraception or expels her intrauterine device/implant, or becomes pregnant
- A female subject has new breast findings (e.g. a palpable mass or abnormal mammography, discharge), or has abnormal vaginal discharge or bleeding
- The subject decides to discontinue study drug treatment, or withdraws consent from the study
- The subject receives a strong CYP3A4 inhibitor (See [Appendix B](#))

- Any medical condition that may jeopardize the subject's safety if study drug is continued, in the investigator's and/or Sponsor's opinion; this may include the development of persistently (2 successive occasions) abnormal thyroid function tests (TSH >10, or TSH > 6 with low free T4; TSH <0.1, or TSH < 0.35 with high free T4); abnormal morning prolactin, cortisol, or corticotropin levels; or signs and symptoms of adrenal insufficiency
- Discontinuation is deemed to be in the best interest of the subject, in the investigator's and/or Sponsor's opinion, including evidence that the subject does not meet inclusion/exclusion criteria intended primarily for safety reasons, or a persistent lack of adherence to study procedures

The Sponsor or designee should be contacted within 24 hours of investigator's awareness of any study drug treatment discontinuation. Investigators should make every effort to contact the Sponsor or designee before discontinuing study drug treatment, if possible.

Subjects who discontinue treatment with study drug prior to completing the treatment period will enter a 5-week follow-up period following the last dose of study drug in addition to a Follow-up visit (see [Section 3.1](#), [Section 6.5.10](#)). Every effort should be made for subjects to complete the Follow-up visit after a subject has discontinued from study drug.

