Vital signs will include measurements of heart rate, blood pressure, respiration rate, and temperature after the subject has been calmly resting (seated or supine) for a minimum of 5 minutes. Vital signs will be assessed as outlined in [Appendix A](#) and at unscheduled study visits when clinically indicated. On study visits when clinical laboratory tests are performed, assessment of vital signs should precede blood draw.

6.2.2 *Physical Examination*

Physical examinations, including height and weight measurements, will be performed as outlined in [Appendix A](#) and at unscheduled study visits when clinically indicated. A complete physical examination will be performed at the screening visit, while subsequent examinations will be abbreviated and targeted to changes in disease activity and/or subjects' symptoms. For female subjects with targeted breast examinations, please perform breast examination after blood draw for clinical laboratory tests.

6.2.3 *Clinical Laboratory Assessments*

Samples for clinical laboratory assessments will be collected as outlined in [Appendix A](#) and at unscheduled study visits when clinically indicated, and analyzed at a central laboratory unless otherwise specified.

Detailed instructions regarding sample collection, preparation, and shipment can be found in the laboratory manual. Laboratory assessments will include the following, and are ideally performed in the morning, particularly at visits with endocrine assessments (Screening, Week 10, Follow-up):

- Hematology: hematocrit, hemoglobin, red blood cell count, red blood cell indices, platelets, white blood cell count, white blood cell differential (neutrophils, lymphocytes, monocytes, basophils, eosinophils)
- Chemistry: sodium, potassium, chloride, bicarbonate, glucose, blood urea nitrogen, creatinine, calcium, phosphorus, magnesium, albumin, uric acid, total protein, ALT, AST, alkaline phosphatase, total bilirubin, lactate dehydrogenase (LDH), lipid panel
- Iron studies: ferritin, serum iron
- Serology: hepatitis B and C serology, HIV
- Serum IgE
- Pregnancy testing: all females of childbearing potential will have a local urine pregnancy test performed. Positive or equivocal urine pregnancy test results will be confirmed by a serum pregnancy test analyzed at a central laboratory
- Endocrine: TSH, free T4, cortisol, corticotropin (adrenocorticotrophic hormone, ACTH), prolactin

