- Reproductive endocrinology (for all female subjects under 55 years of age at consent): serum follicle-stimulating hormone (FSH), luteinizing hormone (LH), estradiol, progesterone, anti-Mullerian hormone (AMH)
- Optional study provided in lab test kits for use at Screening only: endomysial antibody with reflex to titer for subjects with signs or symptoms of dermatitis herpetiformis

- Additional optional studies will be supported through local procedural and/or laboratory assessments, including, but not limited to, skin biopsy and pathology interpretation, urea breath test for *Helicobacter pylori*, and allergy testing (patch, prick, or blood testing); the investigator should discuss the need for such studies with the medical monitor during the Screening period.
- Standard cosyntropin stimulation testing should be performed on subjects with low cortisol level (i.e. < 3.0 mcg/dL); the investigator should discuss low cortisol (and relevant low corticotropin) results with the medical monitor.

6.2.4 *Electrocardiogram*

A standard 12-lead ECG will be performed after the subject has been calmly resting in a supine position for a minimum of 5 minutes before obtaining the ECG. ECGs should precede measurement of vital signs and blood draw for clinical laboratory tests and will be performed as outlined in [Appendix A](#) and at unscheduled study visits when clinically indicated and read centrally. ECG machine and detailed instructions will be provided by the ECG vendor.

6.2.5 *Hospital Anxiety and Depression Scale*

The HADS is a QOL instrument designed to assess the severity of anxiety and depression over the prior week, developed in a hospital outpatient clinic, but also valid in community settings and primary care medical practice. The questionnaire takes approximately 2 to 5 minutes to complete, and is provided in [Appendix F](#). The HADS questionnaire will be collected as outlined in [Appendix A](#).

6.2.6 *Epworth Sleepiness Scale*

The ESS is a QOL instrument intended to measure daytime sleepiness by use of a very short questionnaire. The questionnaire takes approximately 2 to 3 minutes to complete, and is provided in [Appendix G](#). The ESS questionnaire will be collected as outlined in [Appendix A](#).

[figure not shown]
6.3 *Pharmacokinetic Measurements*

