6.9.3 Clinical Laboratory Evaluation

Clinical safety laboratory values will be measured by a central laboratory. Summary statistics for actual values and for changes from baseline will be tabulated for laboratory results by scheduled visit.

Subjects with clinical laboratory values outside of the normal reference range at any post-baseline assessment will be summarized. Shifts from baseline laboratory values will be tabulated, with the exception of most reproductive endocrinology laboratory values.

Serum follicle-stimulating hormone, luteinizing hormone, estradiol, progesterone and anti-mullerian hormone will be summarized separately for women using hormonal contraception/therapies and those not using hormonal contraception/therapies.

By-subject listings of all laboratory data, as well as abnormal laboratory results, will be presented.

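### The SAP's endocrine table shells leave out prolactin, contrary to the SAP's own text on laboratory summaries and shifts

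*SAP*

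**What the plan says.** Protocol version 4.0, Section 6.2.3, defines the endocrine panel as "Endocrine: TSH, free T4, cortisol, corticotropin (adrenocorticotrophic hormone, ACTH), prolactin". It notes that blood is best drawn in the morning, "particularly at visits with endocrine assessments (Screening, Week 10, Follow-up"). The panel carries no sex or age restriction. A separate reproductive panel, for females under 55, consists of "serum follicle-stimulating hormone (FSH), luteinizing hormone (LH), estradiol, progesterone, anti-Mullerian hormone (AMH").

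Protocol Section 5.6 allows study drug to be stopped for a medical condition that may put the subject at risk, in the opinion of the investigator and/or sponsor. Its examples include "abnormal morning prolactin, cortisol, or corticotropin levels".

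Change from baseline in laboratory parameters is a safety endpoint in both documents (protocol Section 3.3.4, SAP Section 5.2). For its analysis, SAP Section 6.9.3 states: "Summary statistics for actual values and for changes from baseline will be tabulated for laboratory results by scheduled visit". On shifts it states: "Shifts from baseline laboratory values will be tabulated, with the exception of most reproductive endocrinology laboratory values". Protocol Section 8.10.2 makes the same commitments without the shift exception.

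The shells then name the tests. The list for summary Table 14.3.1.4.3.1.1 reads "TSH ULTRASENSITIVE”, “THYROXINE, FREE”, “CORTISOL, SERUM RANDOM”, “ACTH, PLASMA”, “ANTI-MULLERIAN HORMONE”, “FSH”, “ESTRADIOL”, “LUTEINIZING HORMONE”, “PROGESTERONE". The list for shift Table 14.3.1.4.3.2 holds TSH, free thyroxine, cortisol (entered as "CORTISOL, SERUM RANDOM"), ACTH and anti-Mullerian hormone. Neither contains prolactin.

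**The concern.** A shell that names its tests is what the programmer works from. Two explicit lists that lack an analyte will normally give two tables that lack it, whatever the general text says. The result would be a collected safety parameter, part of a stated safety endpoint, that is never set out by treatment arm.

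The protocol gives some reason to want that display. Section 5.6 names prolactin in the same phrase as cortisol and corticotropin. Those two are tabulated and prolactin is not. A modest difference in distribution between arms is what a by-arm summary or shift table is meant to show, and it is hard to see in a line-by-line listing.

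**Working it through.** No power, alpha or sample-size figure is involved, so the check is a comparison of lists.

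**Summary table.** Protocol Section 6.2.3 gives 5 endocrine and 5 reproductive analytes, 5 + 5 = 10. Shell 14.3.1.4.3.1.1 covers both panels.

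| Analyte | Protocol panel | In summary shell | In shift shell |
|---|---|---|---|
| TSH | Endocrine | yes | yes |
| Free T4 | Endocrine | yes | yes |
| Cortisol | Endocrine | yes | yes |
| ACTH | Endocrine | yes | yes |
| Prolactin | Endocrine | **no** | **no** |
| AMH | Reproductive | yes | yes |
| FSH | Reproductive | yes | no (stated exception) |
| LH | Reproductive | yes | no (stated exception) |
| Estradiol | Reproductive | yes | no (stated exception) |
| Progesterone | Reproductive | yes | no (stated exception) |

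The summary shell lists 9 of 10, and the missing one is prolactin. SAP Section 6.9.3 states no exception for summaries.

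**Shift table.** The shell lists 5 of 10. Of the 10 − 5 = 5 not listed, four (FSH, LH, estradiol, progesterone) fall under the exception for most reproductive endocrinology values. The fifth is prolactin, which is not in that panel.

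**Could another table carry it?** The other laboratory shells are hematology, chemistry and two reproductive summaries split by use of hormonal contraception or therapy. None lists prolactin, and the table index shows no further laboratory table.

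**Is this one omission among many?** The panels measured again after baseline compare with their summary shells as follows:

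- Hematology: 13 of 13, counting red-cell indices as the three shown (MCH, MCHC, MCV).
- Chemistry: 22 of 22, counting the lipid panel as the four shown (total, HDL and LDL cholesterol, triglycerides).
- Endocrine plus reproductive: 9 of 10.

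In total, 13 + 22 + 9 = 44 of 13 + 22 + 10 = 45 analytes are listed. A single gap in otherwise complete lists looks like an oversight. SAP Section 8 records no change to the planned analyses, so no decision to drop prolactin is documented.

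**How much data is affected?** There are two scheduled post-baseline collections, Week 10 and Follow-up. The shell's 3-week and 5-week columns are alternatives for most subjects, and its latest-follow-up column is derived from them. The schedule also marks laboratory tests at early treatment discontinuation, but its footnote names only Screening, Week 10 and Follow-up for endocrine tests.

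**The case against.** The strongest reply is that the planned analysis already includes prolactin. SAP Section 6.9.3 requires summaries and shifts without exempting it, and nothing in the documents says that a shell overrides the text. The shells may also not be exhaustive: Section 6.9.3 promises a summary of subjects with out-of-range values, and no such table is indexed for any panel. This stands in part. A reader might infer that the sponsor decided not to analyse prolactin, or that it certainly will not be tabulated. The documents support neither. They show text and shells in conflict, with the outcome depending on which one the programmer follows.

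Second, the data are not lost. Listings 16.2.8.2.1 and 16.2.8.2.2 are headed by treatment group and give visit, result, reference range, out-of-range indicator and clinical significance. Out-of-range prolactin values could be counted by arm from them. That is right; what goes missing is the tabulation.

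Third, the clinical weight is easily overstated. Section 5.6 is discretionary, so a reader who infers that a mandatory stopping criterion goes unmonitored would be wrong. The only scheduled on-treatment endocrine sample is at Week 10, the end of treatment. A reader might also tie the omission to the rat findings in protocol Section 1.5.1. Those mammary and reproductive changes occurred above the exposures anticipated for efficacy in humans, with a 2.5-fold margin at the no-effect level for the 5 mg tablet. They were not seen in dogs or mice, and the documents do not link them to prolactin. The point therefore does not rest on them.

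Finally, this is a small correction to descriptive safety tables. True, but a test list that contradicts the section it implements should still be corrected while that costs almost nothing.

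**Conclusion.** The point holds as an inconsistency within the SAP, and between its shells and protocol Section 8.10.2. The text requires by-visit summaries and shifts that include prolactin; the two shells that should deliver them leave it out, and no stated exception covers the omission. Programmed as the shells specify, one of ten collected endocrine and reproductive analytes would have no by-arm summary and no shift, at either of its two scheduled post-baseline collections. The planned size is about 140 randomized subjects per arm; the tables themselves use the Safety population with available samples.

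This rests on two assumptions: that the test lists are meant to be complete, as their wording and their agreement with the other panels suggest, and that programmers will follow them. The consequence is limited to descriptive safety reporting. No hypothesis test, analysis population, decision rule or efficacy conclusion is affected.

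**What to change.** Reconcile the shells with SAP Section 6.9.3 before unblinding:

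- Add PROLACTIN to the test list of Table 14.3.1.4.3.1.1, which then has 9 + 1 = 10 tests, the full endocrine and reproductive set.
- Add PROLACTIN to the test list of Table 14.3.1.4.3.2, which then has 5 + 1 = 6 tests: all five endocrine analytes plus AMH.

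If the omission was intended, say so in Section 6.9.3 and give the reason.

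The cost is one analyte name in two shells. The samples are already scheduled, and no new visit, method or clinical rule is involved.
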